Thirteen orthodontic patients for each group will be selected to wear a removable orthodontic appliance for the study period (**Lima et al., 2006**) and will be instructed for the cleaning protocol according to the manufacturer's instructions.

Inclusion criteria:

- Presence of full upper permanent dentition;
- Well-aligned teeth or mild crowding (less than 3mm);

- No history of sensitivity to any ingredient contained in the cleaning materials;
- Nonsmoker;
- Caries free.

Exclusion criteria:

- Participant taking steroid-based or antibacterial mouthwash or broad-spectrum antibiotics;
- Mouth breather;
- Participant taking medication that reduces salivary flow;
- Pregnant or lactating female (**Albanna *et al.*, 2017**).

All of the study steps were explained to the participants verbally and in writing, written informed consent will be obtained from each participant.

Materials and instruments**Materials used for orthodontic removable appliance fabrication:**

- Acrylic powder and monomer (Orthocryl, Dentaaurum, Ispringen, Germany).
- 0.7 mm stainless steel wire (Spring hard, Dentarum, Ispringrn, Germany).
- Adam's plier.
- Sticky wax.
- Separating medium.
- Cutter.
- Wax knife.
- Mold material.

Materials used for cleaning regimes:

- 1-Brush (dental or denture brush) with chlorhexidine (CHX) toothpaste.
- 2-Chemical cleaning i.e. Lacalut cleaning tablet.
- 3-Combination of brushing with CHX toothpaste and cleaning tablet.

Materials and equipment used form microbial isolation and identification:

1. Calcium alginate swab.
2. Calgon ringer solution.
3. Bijou tube.
4. Glass beads.
5. Phosphate buffered saline (PBS).
6. Anaerobic cabinet.
7. Vortex machine.
8. Culture media.

A. Mitis-Salivarius Agar (MSA): This agar is a commonly used selective medium for isolating and quantifying *S. mutans* in many cariology clinical and epidemiological studies (**Xiao *et al.*, 2016**).

B. Mannitol salt agar: Is a commonly used selective and differential growth medium in microbiology. It contains a high concentration (about 7.5%-10%) of salt (NaCl), making it selective for Gram-positive *Staphylococcus aureus* and *epidermidis* since this level of salt is inhibitory to most other bacteria (**Bachoon *et al.*, 2008**).

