The acrylic tiles (5mm in diameter and 1mm thickness) will be placed and fixed into the holes, created by the metal discs, using sticky wax. The acrylic samples will be randomly seated as shown in figure 3.

The appliance will be sterilized using proper sterilization protocol.

Figure 3: The acrylic base containing the acrylic samples.

Method for biofilm detection

The removable appliance will be assigned randomly and blindly and fitted into the oral cavity of the patient for one week. Each individual will be given a pack containing the cleansing pack and an instruction sheet with a web link describing the cleaning regimen for his/ her appliance. The packs are similar in shape and color and will be prepared by a third person who does not know the purpose of the study. The volunteer will be grouped into three groups:

Group 1: patients will be instructed to brush both sides of the removable appliance once a day for 1 minute before bedtime using the toothbrush and the CHX toothpaste provided and water (**Albanna *et al.*, 2017**).

Group 2: patients will be instructed to immerse the appliance in 150 ml cup with tap water and dissolve one cleansing (**Albanna *et al.*, 2017**) tablet for 20 minutes according to the manufacture instructions.

Group 3: Combination of the chemical and mechanical methods first submitted to the mechanical method, followed by the chemical method (**Oliveira *et al.*, 2009**).

At the end of the study period, the acrylic samples will be removed carefully and applied into a petri dish containing PBS via a sterile tweezer. The samples will be then immersed twice in a 25ml sterile tubes containing

PBS to remove the planktonic bacteria and inserted into 5ml bijou tube containing 1mm PBS and 5 sterile glass beads. The sample will be vortex-mixed for 1 min to disseminate the biofilm and create a homogenous solution. Ten-fold serial dilutions will be carried out in PBS before the samples are plated onto blood agar (BA), to give the total anaerobic count, mitis salivarius agar (MS), a selective agar for streptococci and Mannitol salt agar (MA) for Staphylococci spp. BA and MS plates will be incubated anaerobically for 2-4 days at 37°C using anaerobic cabinet whereas the MA will be incubated for 2 days in aerobic condition. All organisms from both selective and nonselective agars will be distinguished by colony morphology and will be characterized by Gram reaction (**Al Groosh *et al.*, 2011**) and other confirmatory tests.

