Confirmatory test

1. Catalase testing: Catalase is a common enzyme found in nearly all living organisms exposed to oxygen (such as bacteria, plants, and animals) (**Chelikani *et al.*, 2004**). This test demonstrates the presence of catalase, an enzyme that catalysis the release of oxygen from hydrogen peroxide (H₂O₂). The catalase test is mainly used to differentiate between Gram-positive cocci: members of the genus Staphylococcus are catalase-positive, and members of the genera Streptococcus and Enterococcus are catalase-negative (**Whittenbury, 1964**).
2. Coagulase testing: Coagulase is a protein enzyme produced by several microorganisms that enables the conversion of fibrinogen to fibrin. In the research laboratory, it is used to differentiate between different types of Staphylococcus isolates. Importantly, *S. aureus* is generally coagulase-positive (**Ryan and Ray, 2004**).

Statistical analysis

All the data of the tested samples will be collected and analyzed using SPSS (statistical package of social sciences). In this study the following statistics will be used:

Descriptive statistics

- Mean.
- Standard deviation (SD).
- Minimum and maximum values.
- Statistical tables, figures and charts.

Normality test

Data distribution will be tested first using Shapiro-Wilk test to find that whether our collecting data are normally distributed or not.

Inferential statistics

- ANOVA (if the data parametric) or Kruskal Wallis test (if none parametric) to compare the effect of each cleaning agents on biofilm reduction of removable orthodontic appliance and Tukey HSD pot hoc test if there is significant difference between them.
- Independent t-test (if the data parametric) or Mann Whitney test (if none parametric) to compare the effect of each cleaning agents on biofilm reduction on polished and unpolished surface

In the statistical evaluation, the following levels of significance will be used:

Non-significant NS $P > 0.05$

Significant S $0.05 \geq P > 0.01$

Highly significant HS $P \leq 0.01$

Time table:

Duty	Expected time
Patient Identification and allocation	4 months
Intervention period	3 months
Data collection and analysis	2 months
Writing up the thesis	10 months (starting from the beginning of the study)
Total expected time to finish	About 10 to 11 months

Budget and Funding: The study is self-funded

Dissemination: Master Thesis.

References

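### On the parametric branch, ANOVA and Tukey HSD pool one error variance and no rule acts on unequal spread; if one regimen is more variable, power to separate the other two falls

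*Combined protocol and SAP*

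**What the plan says.** Under Method for biofilm detection the design has three arms ("The volunteer will be grouped into three groups"). Sample size gives 13 patients per arm, 39 in all, with no SD, effect size, power or dropout allowance. The outcome is a plated count: "Ten-fold serial dilutions will be carried out in PBS before the samples are plated onto blood agar (BA), to give the total anaerobic count". No transformation of the counts is mentioned.

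Under Statistical analysis, the Normality test paragraph reads "Data distribution will be tested first using Shapiro-Wilk test to find that whether our collecting data are normally distributed or not". Under Inferential statistics, the result of that test decides between ANOVA and Kruskal-Wallis for comparing the regimens, followed by "Tukey HSD pot hoc test if there is significant difference between them". SD, minimum and maximum are listed under Descriptive statistics. The plan names no check of equal variances, no Welch test and no unequal-variance pairwise procedure, and no decision depends on the reported SDs.

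**The concern.** One-way ANOVA and Tukey HSD estimate one error variance from all three arms and use it for every pair. That is efficient when the arms have similar spread. When they do not, the pooled figure is too large for a pair of consistent arms and too small for a pair that includes a sufficiently variable arm. A normality test applied within each arm does not address this, since three normal samples can have very different SDs.

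Unequal spread is plausible here, though not shown. Patients clean the appliance at home, and brushing depends on technique more than soaking does. A very effective regimen could also compress counts towards the floor.

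The research question asks which method is most effective, and the pairwise comparisons answer it. If one regimen is erratic, its variance enters the comparison of the other two, and a real difference between those two can be missed.

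**Working it through.** **Inputs from the documents.** Three arms, 13 per arm, two-tier significance labels starting at P = 0.05, ANOVA then Tukey HSD on the parametric branch.

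**Inputs assumed.** Normal data on the analysis scale; SD ratios 1:1:1 to 1:1:3; a true difference of 1.2 SD between the two consistent arms, with the third mean midway. SD here means the SD of a consistent arm.

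**The plan's own figure.** The 13 per arm cannot be reproduced, because no inputs are given. For scale only, an unadjusted two-arm comparison at two-sided 5% and 80% power needs 2 × (2.80/1.10)² ≈ 13 per arm for a 1.1 SD difference. A 1.2 SD effect is therefore near what this size can detect.

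**Mechanism.** With equal arms the pooled variance is the mean of the three variances, and Tukey's least significant difference is q × √(pooled variance/13), with q(0.95; 3, 36) = 3.457.

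- 1:1:1: pooled 1; 3.457 × √(1/13) = 0.96
- 1:1:1.5: pooled (1 + 1 + 2.25)/3 = 1.42; threshold 1.14
- 1:1:2: pooled (1 + 1 + 4)/3 = 2; threshold 1.36
- 1:1:3: pooled (1 + 1 + 9)/3 = 3.67; threshold 1.84

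The true standard error for the two consistent arms stays at √(2/13) = 0.39 throughout. At 1:1:2 the threshold already exceeds the true difference of 1.2. For a pair with the variable arm at 1:1:2, the correct average variance is (1 + 4)/2 = 2.5 against the pooled 2, so Tukey is slightly too lenient.

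**Simulation** (200,000 trials per scenario). Tukey power requires a significant ANOVA first, as planned; dropping that gate adds less than 2 points. Games-Howell is ungated. The error columns are for no true difference, with Tukey ungated.

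| SD ratio | Tukey power, consistent pair | Games-Howell power | Tukey error, consistent pair | Tukey error, each other pair | Tukey family-wise error |
|---|---|---|---|---|---|
| 1:1:1 | 71% | 71% | 1.9% | 1.9% | 5.0% |
| 1:1:1.5 | 55% | 71% | 0.7% | 2.9% | 5.3% |
| 1:1:2 | 36% | 71% | 0.2% | 3.8% | 6.1% |
| 1:1:3 | 10% | 70-71% | 0.01% | 5.1% | 7.1% |

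ANOVA's own type I error rises from 5.0% to 7.7% over the same ratios. With the gate, Tukey's family-wise error is about 5.7% at 1:1:2 and 6.5-6.8% at 1:1:3. Over the same ratios Welch's ANOVA stays at 4.8-5.0%, and Games-Howell's family-wise error at about 5%.

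**Cost when spreads are equal.** Games-Howell power is 70.6%, against 71.4% for gated and 72.8% for ungated Tukey: 1 to 2 points.

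**Would the planned check catch it?** Shapiro-Wilk run per arm flagged at least one arm in 13% of trials both at 1:1:1 and at 1:1:2, so it does not respond to spread.

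**Would a variance pre-test do?** Levene's test at 13 per arm detects 1:1:1.5, 1:1:2 and 1:1:3 with probability 26%, 62% and 93%. It misses most moderate cases.

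**Unequal arms.** If the most variable arm fell to 9 patients (an assumed loss), ANOVA error would be 7.1%, 9.5% and 12.6% at the three unequal ratios. Welch's ANOVA stays at 4.9-5.1%.

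**The case against.** The strongest objection is that this branch may not be reached. The plan mentions no log transform, and untransformed log-normal counts (assumed log10 SD 0.3 to 1) fail Shapiro-Wilk in at least one arm in 88-100% of simulated trials. They go to Kruskal-Wallis, which pools no error variance and whose error under unequal spread was 5.3-5.8%. This stands, and it confines the point to the parametric branch. That branch is still a planned analysis, and a likely one if counts are put on a log scale.

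Second, the likely causes of unequal spread also disturb normality. In simulation with assumed values, an arm centred on the detection limit was flagged by per-arm Shapiro-Wilk in 95% of trials (67% with the mean 0.5 SD above the limit, 27% at 1 SD). An adherence mixture with a 3-log benefit was flagged in 76-84%, and with a 2-log benefit in 30-44%. The plan also does not say that the test is run per arm. On pooled residuals it flagged 20% of trials at 1:1:2 and 55% at 1:1:3, against 5% with equal SDs. So the planned check is not always blind, though in the milder cases it often lets the data through.

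Third, a reader might infer that every pairwise verdict is distorted, or that unequal spread would go unseen. The documents support neither. Distortion needs unequal spread and differs by pair: with variances 1, 2 and 3, the first and third arms average 2, which equals the pooled value, so that pair is about right. SDs will be reported; what is missing is a rule that uses them.

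Finally, ANOVA with Tukey in equal arms is conventional, and the loss becomes large only if one arm is markedly more variable. Both points stand.

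**Conclusion.** The point holds for the parametric branch, as a cheap improvement rather than the correction of an error. If one regimen is 1.5, 2 or 3 times as variable as the other two, power to separate those two at a 1.2 SD difference is about 55%, 36% and 10% with the planned method, against about 70% with Games-Howell. A reader might infer a serious false-positive problem. With the planned equal arms there is none: family-wise error is about 5-7%. Overall error would become a concern mainly if losses fell on the most variable arm.

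These figures assume normal data on the analysis scale and SD ratios that the documents neither give nor rule out, so the actual effect in this trial is unknown. Nothing here applies to data analysed by Kruskal-Wallis.

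**What to change.** Under Inferential statistics, for the parametric branch, replace ANOVA and Tukey HSD with Welch's ANOVA and Games-Howell pairwise comparisons on one value per patient. State that they are used without a variance pre-test. Both are options in the SPSS one-way ANOVA procedure, and the plan already names SPSS.

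The cost is one sentence in the analysis section and about 1-2 percentage points of pairwise power if the variances turn out equal. Sample size and data collection do not change.

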Some studies have already been conducted in order to investigate the effects of different cleaning protocols for acrylic removable orthodontic appliances and may also help to reduce the risk of oral diseases related to biofilm growth, some different processes have been described such as denture cleaners, enzymatic solutions, chlorhexidine, sodium hypochlorite, or homemade solutions containing vinegar or citric acid (**Eichenauer *et al.*, 2011**). The two major approaches used for denture cleaning are mechanical and chemical methods. Mechanical methods include brushing (using water, soap, toothpaste, or abrasives) and ultrasonic treatment. Mechanical cleaning with brushes is inexpensive and common, but elderly and disabled patients might face difficulties with this method because of poor motor coordination, poor dexterity, and low motivation. There is evidence that mechanical cleaning with toothpastes can result in significant wear of conventional acrylic resins. Chemical method includes immersion of dentures in different cleansing solutions. Immersion in cleansing solution is an inexpensive, easy, and comfortable alternative procedure. Moreover, the cleansing solution can reach undercuts of the denture base that are difficult to clean mechanically, resulting in more efficient cleaning (**Schwindling *et al.*, 2014**).

No study is conducted to evaluate the most effective method used to remove biofilm from removable orthodontic appliance.

Research question:

What is the most effective method of cleaning an acrylic based removable orthodontic appliance?

Research hypothesis

The null hypothesis: There is no difference between the different methods of cleaning acrylic based removable orthodontic appliances.

Aims of the study:

The aims of the current study are:

1. To evaluate the effects of different cleaning regimes i.e. chemical and mechanical on biofilm formation of an acrylic based removable orthodontic appliance.
2. To find out if surface modification i.e. polished acrylic fitting surface, have an impact on cleaning the biofilm formation.

Methodology

Study design:

An in vivo study.

Setting:

It is double-blind, parallel, randomized clinical trial conducted in the orthodontic clinic after obtaining the ethical approval from the ethics committee of the department.

Subjects:

Orthodontic patient will be selected to wear a removable appliance for the study period.

Sample size:

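### Tukey HSD is the only post hoc test named, and as written it also follows Kruskal-Wallis; on skewed raw colony counts it can miss true differences between cleaning methods

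*Combined protocol and SAP*

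**What the plan says.** The Research question section asks: "What is the most effective method of cleaning an acrylic based removable orthodontic appliance". Under Statistical analysis, the Normality test section gives the rule for choosing the test: "Data distribution will be tested first using Shapiro-Wilk test to find that whether our collecting data are normally distributed or not". It does not say whether this is applied per group or to residuals, or to raw or transformed values.

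The Inferential statistics section then plans "ANOVA (if the data parametric) or Kruskal Wallis test (if none parametric) to compare the effect of each cleaning agents on biofilm reduction" and continues, in the same sentence, "and Tukey HSD pot hoc test if there is significant difference between them". The next bullet names an independent t-test or "Mann Whitney test (if none parametric) to compare the effect of each cleaning agents on biofilm reduction on polished and unpolished surface". That is a surface comparison, not a comparison of regimens. No other post hoc test appears in the document.

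The outcome is a colony count. The Method for biofilm detection section has samples serially diluted and "plated onto blood agar (BA), to give the total anaerobic count", with two selective media alongside. No section states a transformation or an analysis scale. The planned summaries are the mean, SD, minimum and maximum. On size, the Sample size section says: "Thirteen orthodontic patients for each group will be selected to wear a removable orthodontic appliance".

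**The concern.** With three regimens, a significant omnibus test shows only that they are not all alike. Which one is best is decided at the pairwise step, so that step carries the answer to the research question.

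Tukey HSD compares arithmetic means using one pooled variance. Kruskal-Wallis is reached only when the data have been judged non-normal, which is where Tukey's assumptions fail. On right-skewed counts the SD rises with the mean, so the regimen with the highest counts dominates the pooled variance. The yardstick for every pair is then set by the worst regimen, and a real difference between the two better regimens can disappear. The trial could report a significant overall test and still be unable to name the best method.

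The alternative reading, Tukey for ANOVA only, leaves the Kruskal-Wallis branch without a pairwise test of the regimens. The test would then be picked after the data are seen.

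**Working it through.** **Inputs from the plan.** Three groups, 13 patients each, alpha 0.05, the tests quoted above. The figure of 13 comes from a cited study. It cannot be reproduced, because no SD, effect size or power is given.

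**Assumptions (not in the plan).** Log-normal counts; one value per patient; equal within-group SD of the log10 count, varied from 0.2 to 1.0; true differences of 0.5 to 2 log10.

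**1. How likely is the Kruskal-Wallis branch?** In simulation, Shapiro-Wilk on raw counts rejects in at least one of the three groups in 65% of trials at SD 0.2, 88% at 0.3, 97% at 0.4 and over 99% from 0.5.

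**2. Why raw-count Tukey loses the better regimens.** Take SD 0.5 and true steps 0, -0.5, -1 log10, with the mean of the highest group set to 1.
- Means: 1, 10^-0.5 = 0.316, 10^-1 = 0.100.
- Squared coefficient of variation: exp[(0.5 × ln 10)²] - 1 = exp(1.325) - 1 = 2.76.
- Pooled variance: 2.76 × (1 + 0.1 + 0.01)/3 = 1.02, so the pooled SD is 1.01. The highest group supplies 1/1.11 = 90% of it.
- Tukey threshold (critical q 3.457; 3 groups, 36 df): 3.457 × 1.01/√13 = 0.97.
- True difference between the two better regimens: 0.316 - 0.100 = 0.216, under a quarter of the threshold.
- On the log10 scale the threshold is 3.457 × 0.5/√13 = 0.479, against a true difference of 0.5.

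These use expected values; the simulations below allow for sampling variation.

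**3. Power to separate the two better regimens** (significant omnibus test and significant pair; 4,000 trials per cell, simulation standard error at most √(0.25/4000) = 0.8 points):

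| True pattern (log10) | Method | SD 0.2 | 0.3 | 0.5 | 0.8 | 1.0 |
|---|---|---|---|---|---|---|
| 0, -0.5, -1 | Kruskal-Wallis, raw Tukey | 26% | 6% | 1.5% | 0.5% | 0.3% |
| | Kruskal-Wallis, Dunn-Holm | 100% | 87% | 43% | 16% | 12% |
| | ANOVA, Tukey on log10 | 100% | 96% | 55% | 21% | 14% |
| 0, -1, -2 | Kruskal-Wallis, raw Tukey | about 0.1% or less at every SD | | | | |
| | Kruskal-Wallis, Dunn-Holm | 100% | 100% | 96% | 64% | 42% |
| | ANOVA, Tukey on log10 | 100% | 100% | 100% | 76% | 55% |

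**4. Power per true pair when one regimen is 1 log10 lower than two equal ones** (20,000 trials per cell; Tukey on log10 counts here without an omnibus gate):

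| Method | SD 0.3 | 0.5 | 0.75 | 1.0 |
|---|---|---|---|---|
| Kruskal-Wallis, raw Tukey | 94% | 42% | 10% | 3% |
| Kruskal-Wallis, Dunn-Holm | 100% | 99% | 78% | 49% |
| Tukey on log10 | 100% | 100% | 82% | 55% |

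In this pattern a significant Kruskal-Wallis is followed by no significant raw Tukey pair at all in 0.6%, 32%, 78% and 90% of trials.

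**5. False positives.** With no true difference, raw Tukey taken alone flags some pair in 4.6% of trials at SD 0.2 and 1.1% at SD 1.0. Gated by Kruskal-Wallis, the rate is 2.6% at SD 0.3 and 0.6% at SD 1.0. With one regimen 1 log10 lower, raw Tukey wrongly separates the two equal regimens in 5.6%, 4.6% and 4.0% of trials at SD 0.2, 0.3 and 0.5. That is close to nominal.

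**The case against.** - **Reading.** The sentence is loosely written, and Tukey may be meant for ANOVA only. The power figures for raw Tukey after Kruskal-Wallis would then not apply. The gap would remain as an omission, because no pairwise regimen test exists in that branch.
- **Scale.** Skewed, untransformed counts are an inference. If the investigators log the counts before testing normality, Tukey after ANOVA is sound and most of the loss goes. This is fair, but nothing in the plan says so, and the rank branch would still need its own test.
- **Choice of contrast.** Separating the two better regimens is the comparison least favourable to raw Tukey. With steps 0, -0.5, -1 at SD 0.5, raw Tukey separates the highest from the middle regimen about as often as Dunn-Holm (45% against 43%). It separates highest from lowest in 79% of trials against 99%. This stands. The harm is concentrated where the best method is to be named, and it is not uniform.
- **Low spread.** With one regimen 1 log10 lower and SD 0.3 or less, each true pair is found at least 94% of the time. This also stands.
- **Unit of analysis.** One value per patient is assumed. Each appliance has recesses for four tiles, three media are used, and the plan analyses data from all tested samples. If tiles were treated as independent, neither the power nor the false-positive figures would carry over.
- **False positives.** Raw Tukey is conservative when no regimens differ, but not in every configuration. The excess seen is too small to change the conclusion.

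**Conclusion.** The concern holds. On either reading, the plan lacks a suitable pairwise comparison of the three regimens after Kruskal-Wallis, and that follows from the text alone. Under log-normal raw counts this is the branch most likely to be used.

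The size of the loss depends on the assumed spread and pattern. It is slight at SD 0.3 or less when a single regimen stands 1 log10 below the others, and large from SD 0.5 upward. When all three regimens differ, separation of the two better ones is poor at every SD examined: 26% at best for 0.5 log10 steps, and about 0.1% or less for 1 log10 steps. These are illustrations under stated assumptions, not forecasts for this trial. The consequence is a reduced chance of naming the best method, not a material rise in false claims. It should be corrected before analysis.

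**What to change.** Amend the Statistical analysis section to state that:

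1. Counts are analysed as log10(CFU+1), with the handling of zero or below-detection plates given, because the added 1 matters when many plates are empty. Normality is assessed on this scale, and the regimens are compared by ANOVA followed by Tukey HSD.
2. If the log10 data are still non-normal, Kruskal-Wallis is followed by Dunn's test with Holm adjustment, or another multiplicity-adjusted rank-based pairwise test named in advance.
3. Tukey HSD is not applied to raw counts after Kruskal-Wallis.

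The same edit should state the analysis unit, since the power of any of these tests depends on it.

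The cost is wording only, with no extra patients, samples or laboratory work. The one drawback is that results are reported as log10 differences, that is ratios, rather than differences in raw mean counts.

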C. Blood agar: is enriched medium used to culture those bacteria or microbes that do not grow easily. Such bacteria are called “fastidious” as they demand a special enriched nutritional environment as compared to the routine bacteria (**Sirois, 2020**).

Other materials:

- 1- Rubber bowl
- 2- Type IV stone
- 3- Gloves
- 4- Masks

5- Plastic petri dish

Procedure

Construction of acrylic samples with different surface texture:

Acrylic samples i.e. tiles of different surface texture will be made. An acrylic sheet of 1 mm thickness will be made using a mold with technique as shown in figure 3.

[figure not shown]

Figure 1: Acrylic samples made from polished and unpolished acrylic sheet.

A half of the sheet will be polished using a conventional polishing technique until a glossy surface appears, whereas, the remaining will be kept without modification. Tiles of 5mm in diameter will be bored using a trephine bur on both sides of the acrylic sheets and each set of tiles i.e. the polished and unpolished samples, will be color coated from its seated surface.

Construction of upper removable orthodontic appliance

An impression will be taken to the maxillary arch using alginate impression material (Hydrogum 5, Zhermack, Badia Polesine, Italy). The negative replica is then poured using type IV stone to make a study model. Four metal discs (5mm in diameter and 1.2mm thickness) will be placed on both sides of the palate as seen in figure 2; A.

[figure not shown]

Figure 2: Construction of the acrylic based orthodontic appliance. A, Study model with acrylic tiles; B, Fitting surface of the acrylic removable appliance.

The wire framework of the removable appliance will be fabricated using a 0.7 mm in diameter stainless steel wire (Spring hard, Dentarum, Ispringen, Germany) to make Adam's clasps on upper first premolars and molars to retain the appliance.

After applying a separating medium, an acrylic base will be fabricated using the orthodontic acrylic powder and liquid (Orthocryle, Dentaurum, Ispringen, German) with a ratio of (2.5 parts powder to 1 part liquid) according to the manufacturer's instruction. Before setting, a sprue or chimney like structure will be created through the acrylic dough to facilitate the metal discs and acrylic sample removal. The appliance then will be removed and the metal tiles will be dislodged using metal pin (Figure 2; B).

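### Polished and unpolished tiles appear to share one patient's appliance, yet the surface comparison (Aim 2) is assigned an unpaired test, so its standard error is generally wrong

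*Combined protocol and SAP*

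**What the plan says.** Aim 2 (Aims of the study) is "To find out if surface modification i.e. polished acrylic fitting surface, have an impact on cleaning the biofilm formation". The test given for it under Inferential statistics is "Independent t-test (if the data parametric) or Mann Whitney test (if none parametric) to compare the effect of each cleaning agents on biofilm reduction"; the sentence ends by naming "biofilm reduction on polished and unpolished surface" as what is compared. It cannot sensibly be a comparison of regimens, because there are three of them and the preceding bullet already covers them with ANOVA or Kruskal-Wallis.

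The layout comes from the Procedure:

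- Construction of acrylic samples: "each set of tiles i.e. the polished and unpolished samples, will be color coated from its seated surface".
- Construction of the appliance: "Four metal discs (5mm in diameter and 1.2mm thickness) will be placed on both sides of the palate". The holes these discs leave are then filled with acrylic tiles.
- Tile placement: "The acrylic samples will be randomly seated as shown in figure 3".
- Method for biofilm detection: "The volunteer will be grouped into three groups". The groups are brushing, cleansing tablet, and both. None is defined by surface.

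On the unit of analysis the plan says only "All the data of the tested samples will be collected and analyzed using SPSS". No paired test, mixed model or averaging of tiles within patient appears anywhere.

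**The concern.** Colour coding and random seating have an obvious purpose if unlike tiles share an appliance, and little purpose if all four tiles are alike. Read this way, surface is a split-mouth factor. Tiles in one mouth share saliva, flora, hygiene and adherence to the regimen for a week, so their counts are likely to be positively correlated.

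The independent t-test and the Mann-Whitney test both assume unrelated observations. Applied to paired data, they use the wrong standard error for the only planned test of one of the two stated aims. Depending on the unit entered, a real polishing effect may be missed or a false one declared. With 13 patients per regimen there is little information to spare.

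**Working it through.** **Inputs from the documents.** 13 patients per regimen (Sample size), four tile positions per appliance, significance at 0.05 (two-sided assumed). The 13 is taken from a cited study without effect size, SD or power, so it cannot be reproduced.

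**Assumed inputs.** Two tiles of each surface per appliance, tile SD of 1 on a log scale, and a range of correlations and effects. None of these is stated in the documents.

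**1. One value per surface per patient.** Let r be the correlation between a patient's two values.

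- True variance of the mean difference: 2·SD²·(1 - r)/13
- Variance the independent test uses: 2·SD²/13
- Ratio of standard errors, used to true: 1/sqrt(1 - r)

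Simulation with 200,000 replicates; the last column is from the noncentral t:

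| r | SE ratio | Type I error, unpaired t | Power at 0.8 SD, unpaired / paired | Difference detectable at 80% power, paired |
|---|---|---|---|---|
| 0 | 1.00 | 4.9% | 50% / 47% | 1.20 SD |
| 0.3 | 1.20 | 2.2% | 50% / 61% | 1.00 SD |
| 0.5 | 1.41 | 0.8% | 50% / 75% | 0.85 SD |
| 0.7 | 1.83 | 0.2% | 51% / 93% | 0.66 SD |

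The nominal detectable difference for the independent test, 13 v 13, is 1.15 SD.

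**2. Means of two tiles per surface, one common tile correlation.** The scale differs from step 1. Two-tile means correlate at 2r/(1 + r), so tile correlations of 0.3, 0.5 and 0.7 give 0.46, 0.67 and 0.82. Power at a 0.6 SD effect (100,000 replicates for the t-tests, 20,000 for the rank tests):

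| Tile correlation | 0 | 0.1 | 0.3 | 0.5 | 0.7 |
|---|---|---|---|---|---|
| Independent t | 55% | 51% | 43% | 35% | 26% |
| Paired t | 51% | 56% | 66% | 80% | 95% |
| Mann-Whitney | 50% | 46% | 38% | 31% | 24% |
| Wilcoxon signed-rank | 49% | 53% | 63% | 78% | 94% |

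The noncentral t confirms the paired row: 51.2, 55.4, 66.1, 80.2 and 95.1%.

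**3. Individual tiles as the unit (26 v 26).** Let r_same and r_diff be the correlations between tiles of the same and of different surface in one patient.

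- True variance of the difference: (1 + r_same - 2·r_diff)/13
- Variance the independent test assumes: about 2/26 = 1/13
- Ratio, true to assumed: about 1 + r_same - 2·r_diff

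The ratio exceeds 1, and the test is liberal, when r_same is more than twice r_diff:

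| r_same / r_diff | Ratio | Type I error |
|---|---|---|
| 0.5 / 0.5 | 1 + 0.5 - 1.0 = 0.5 | 0.8% |
| 0.5 / 0.2 | 1 + 0.5 - 0.4 = 1.1 | 6.5% |
| 0.7 / 0.3 | 1 + 0.7 - 0.6 = 1.1 | 6.9% |
| 0.5 / 0.1 | 1 + 0.5 - 0.2 = 1.3 | 9.0% |

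The paired t-test on patient means held 4.9 to 5.1% in every null scenario of this simulation.

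**The case against.** The premise is inferred. No sentence says that one appliance holds both surfaces, and the arrangement is left to a figure that is not available. If each appliance carried a single surface, the independent test would be right at patient level. This is a real limit, but it is the less natural reading, because no allocation of surface to patients is described. The missing figure may also show how many tiles of each type are used, so the absence of that count from the text is not held against the plan.

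Every size above rests on assumed inputs. In the likeliest case (positive correlation, one value per surface) the error is conservative, costing power rather than producing false claims. The liberal case needs tile-level analysis and a particular correlation pattern. At zero correlation the paired t-test is slightly weaker (51% against 55% in step 2). All of this stands, and it limits what can be said about size and direction.

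It may also be said that the research question and null hypothesis concern cleaning methods only, and that the regimen comparison is untouched. That is so, but surface is one of only two stated aims and this is its only planned test. The mismatch between test and apparent design does not depend on the assumed values.

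**Conclusion.** The concern holds: on the natural reading of the Procedure, the test named for Aim 2 does not match the design. The standard error is right only if tiles within a patient are uncorrelated or, at tile level, if the correlations happen to balance.

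With one value per surface and positive correlation, the test is conservative and can lose much of its power. With individual tiles as the unit it may be too conservative or too liberal, and the plan does not say which unit applies. The conclusion rests on both surfaces being in each appliance; its size rests on correlations, an SD and effects that the documents do not give. This should be corrected before the analysis.

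**What to change.** In Inferential statistics, replace the independent t-test and Mann-Whitney test for surface with a paired analysis. Average log10 CFU by patient and surface, check normality on the within-patient differences, and use a paired t-test, or Wilcoxon signed-rank if non-parametric, within each regimen.

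Alternatively, fit a linear mixed model with a random patient effect and terms for surface, regimen and their interaction. If individual tiles are entered, add a patient-by-surface random term. The interaction addresses whether polishing changes how well cleaning works, which is how Aim 2 is worded, and the model copes with unequal tile mixes. It is an option: the paired test is enough to correct the error.

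State the unit of analysis. Unless the figure already shows it, add a sentence on how many tiles of each surface an appliance carries. If any appliance carries only one surface, say how surface is allocated to patients.

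The cost is a short edit to the statistics section and at most a sentence on tile composition. No extra patients or data are needed, and SPSS supports these analyses.
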